## 1 Protocol Summary

## 1.1 Synopsis

**Protocol Title:** Phase 2 Randomized Double-Blind Placebo-Controlled 4-Period Single-Dose Crossover Factorial Study to Evaluate the Contribution of the Individual Drug Components to the Efficacy of the Combination of Atomoxetine and R-oxybutynin in Obstructive Sleep Apnea

**Sponsor Study No.:** APC-003

Phase: 2

**Sponsor:** Apnimed, Inc.

#### **Rationale:**

Previous studies conducted by the sponsor (under IND 136752) and academic investigators indicate that the combination drug composed of atomoxetine and oxybutynin (designated AD036) is effective for the treatment of obstructive sleep apnea (OSA). Oxybutynin is a racemic mixture of R and S enantiomers. Oxybutynin is approved in the U.S. for overactive bladder. Efficacy of oxybutynin in overactive bladder may result both from antimuscarinic effects and smooth muscle spasmolytic effects. The contribution to efficacy of oxybutynin in OSA is believed to be related to the antimuscarinic effects, whereas spasmolytic effects may lead to effects on the bladder that are undesirable in typical OSA patients. The R-enantiomer of oxybutynin has been shown to confer the antimuscarinic effect of oxybutynin, whereas the spasmolytic effects (and other effects on calcium channel antagonism and local anesthetic effects) are non-stereoselective properties of both the enantiomers. Apnimed therefore believes that the combination of the R-enantiomer of oxybutynin with atomoxetine, designated AD109, may have an improved safety and efficacy profile in OSA compared to the combination with the racemate of oxybutynin.

This factorial study is designed to demonstrate that both atomoxetine and R-oxybutynin contribute to the efficacy of AD109 in OSA, and thus to fulfill FDA requirements for approval of combination drugs under 21 CFR Subpart B Section 300.50 Fixed-combination prescription drugs for humans.

6 January 2021 6 of 50 V2.0

#### **Overall Design:**

Study APC-003 is a randomized, double blind, placebo-controlled, 4-period, single-dose crossover factorial study in patients with OSA. A screening visit and polysomnographic (PSG) exam will be conducted to establish that each participant meets study enrollment criteria. Each participant will then receive a single dose of each of the following during 4 overnight PSG exams, each separated by a one week washout period:

- Atomoxetine 75 mg + R-oxybutynin 2.5 mg (AD109)
- Atomoxetine 75 mg
- R-oxybutynin 2.5 mg
- Placebo

The primary hypothesis of the crossover study is that AD109 is superior to each of the other 3 arms, on the endpoint of Hypoxic Burden (HB), a measure of the depth and duration of the ventilatory disturbance in OSA.

#### **Number of Participants:**

A total of 58 participants will be enrolled.

#### **Study Duration:**

The overall study duration will be up to 14 weeks, as follows:

- Screening, up to 4 weeks;
- 4-period crossover, up to 8 weeks;
- End of Study Evaluation, 2 weeks post crossover period

6 January 2021 7 of 50 V2.0

## 1.2 Schedule of Activities (SoA)

 Table 1
 Schedule of Activities

	Screening		4-Way Crossover Period Visit 3-6						End of Study Evaluation 		
Procedures	Daytime V1	PSG V2	PSG V3	Wash- out 	PSG V4	Wash- out	PSG V5	Wash- out	PSG V6	Wash- out	
Trial Day (Visit Window)	Up to 4 w	veeks				Up to 8	weeks				2 weeks post V6 ± 3 days
Informed consent	X										
Non-PSG enrollment criteria	X										
Demography	X										
ESS	X										
Physical exam	X										
Medical history	X										
Clinical laboratory test	X										
Pregnancy test 	X										
12 Lead ECG	X										
PSG Exam		$X^4$	X		X		X		X		
Randomization 			X								
Administration of study treatment 			X		X		X		X		
DSST 			X		X		X		X		
Vital signs 	X	X	X		X		X		X		
AE/SAE monitoring			X	X	X	X	X	X	X	X	X
Prior/concomitant medication monitoring	X	X	X	X	X	X	X	X	X	X	X

Abbreviations: AE = adverse event; DSST = Digit Symbol Substitution Test; ECG = electrocardiogram; ESS = Epworth Sleepiness Scale; PSG = polysomnography; SAE = serious adverse event; WOCBP = women of childbearing potential.

<sup>1 Can be conducted remotely. For patients enrolling in Study APC-003-OLE, can be conducted concurrently with first visit of Study APC-003-OLE.

<sup>2 Each washout period is a minimum of 7 days

<sup>3 WOCBP only

<sup>4 A PSG conducted by the study site within 6 months that meets PSG enrollment criteria can take the place of a screening PSG and V2

<sup>5 Randomization occurs when participant meets enrollment criteria up to the time of the first crossover period

<sup>6 Study medication administered immediately before lights out

<sup>7 Administer at similar time after awakening after each crossover PSG, approximately 1 hour after awakening

<sup>8 Vital signs include the following: seated blood pressure, pulse, respiratory rate; vital signs on PSG nights taken after admission to PSG lab

#### 2 Introduction

## 2.1 Study Rationale

Previous studies conducted by the sponsor (under IND 136752) and academic investigators indicate that the combination drug composed of atomoxetine and oxybutynin (designated AD036) is effective for the treatment of obstructive sleep apnea (OSA). Oxybutynin is a racemic mixture of R and S enantiomers. Oxybutynin is approved in the U.S. for overactive bladder. Efficacy in overactive bladder may result both from antimuscarinic effects of oxybutynin and smooth muscle spasmolytic effects. The contribution to efficacy of oxybutynin in OSA is believed to be related to antimuscarinic effects, whereas spasmolytic effects may lead to effects on the bladder that are undesirable in typical OSA patients. The R-enantiomer of oxybutynin has been shown to confer the antimuscarinic effect of oxybutynin, whereas the spasmolytic effects (and other effects on calcium channel antagonism and local anesthetic effects) are non-stereoselective properties of both the enantiomers. Apnimed therefore believes that the combination of the R-enantiomer of oxybutynin with atomoxetine, designated AD109, may have an improved safety and efficacy profile in OSA compared to the combination with the racemate of oxybutynin.

This factorial study is designed to demonstrate that both atomoxetine and R-oxybutynin contribute to the efficacy of AD109 in OSA, and thus to fulfill FDA requirements for approval of combination drugs under 21 CFR Subpart B Section 300.50 Fixed-combination prescription drugs for humans.

# 2.2 Background

# 2.2.1 Obstructive Sleep Apnea

The National Commission on Sleep Disorders Research identified sleep disorders as a major public health burden. OSA is the most common and serious of these sleep disorders and affects approximately 20 million people in the United States (US), with approximately 13% of men and 6% of women affected (Peppard et al, 2013). OSA is characterized by repetitive collapse or 'obstruction' of the pharyngeal airway during sleep, manifesting as repetitive episodes of hypopnea (i.e., shallow breathing) or apnea (i.e., paused breathing). These episodes of hypopnea or apnea may lead to arousal from sleep, sleep fragmentation, excessive daytime sleepiness, and/or neuropsychological impairment.

Research has shown that a number of pathogenic factors, or traits, contribute to the development of OSA (Eckert et al, 2013; Wellman et al, 2011; Wellman et al, 2013; Younes, 2003). The most important factors are the presence of an anatomically small, collapsible upper airway and a loss of pharyngeal muscle tone or responsiveness during sleep.

Long-term, OSA is associated with increased mortality and a number of adverse cardiovascular, neurocognitive, metabolic, and daytime functioning consequences (Somers et al, 1995; Nieto et al, 2000; Brooks et al, 1997; Peppard et al, 2000; Hung et al, 1990; Wessendorf et al, 2000; Hoffstein, 1994; Shahar et al, 2001; Redline et al, 1997; Findley et al, 1988).

#### 2.2.2 Unmet Medical Need

Treatment for OSA changed little over the past 40 years, with the overwhelming majority of patients treated with positive airway pressure, the most common of which is continuous positive airway pressure (CPAP), provided by a machine that mechanically maintains an open airway. Other treatments, such as pharyngeal surgery, mandibular advancement devices, and implantable nerve stimulators, were developed to address the anatomical predisposition to collapse; however, they have shown limited efficacy for niche populations.

While CPAP and related therapies are effective in improving sleep characteristics and oxygenation, many, perhaps most, patients find these devices uncomfortable or intolerable, and most estimates indicate that fewer than 50% of patients prescribed CPAP use it more than 4 hours per night, if at all (Weaver and Sawyer, 2010). Efforts to develop pharmacologic therapies, such as antidepressants, stimulants, and hormonal agents, for the treatment of OSA have been ongoing for at least 20 years, with no success thus far.

As many patients cannot use CPAP because they find it intolerable, this represents a significant health concern, as OSA is associated with numerous co-morbidities and increased mortality. Alternative options, such as drugs that activate the pharyngeal muscles, are needed.

## 2.2.3 Biological Rationale

AD109 is a new fixed dose drug combination of atomoxetine and R-oxybutynin being developed for OSA. Atomoxetine is a pre-synaptic norepinephrine reuptake inhibitor indicated for the treatment of attention deficit hyperactivity disorder in children and adults. R-oxybutynin has never been marketed, but racemic oxybutynin is approved as an antispasmodic drug that inhibits the muscarinic action of acetylcholine on smooth muscle and is indicated for the treatment of symptoms of bladder instability associated with voiding in patients with uninhibited neurogenic

or reflex neurogenic bladder such as urgency, frequency, urinary leakage, urge incontinence and dysuria.

Efficacy of oxybutynin in overactive bladder may result both from antimuscarinic effects of oxybutynin and smooth muscle spasmolytic effects. The contribution to efficacy of oxybutynin in OSA is believed to be related to antimuscarinic effects, whereas spasmolytic effects may lead to effects on the bladder that are undesirable in typical OSA patients. The R-enantiomer of oxybutynin has been shown to confer the antimuscarinic effect of oxybutynin, whereas the spasmolytic effects (and other effects on calcium channel antagonism and local anesthetic effects) are non-stereoselective properties of both the enantiomers. Apnimed therefore believes that the combination of the R-enantiomer of oxybutynin with atomoxetine may have an improved safety and efficacy profile in OSA compared to the combination with the racemate of oxybutynin. This factorial study, APC-003, is designed to demonstrate that both atomoxetine and R-oxybutynin contribute to the efficacy of AD109 in OSA.

## 3 Endpoints

	Endpoints
Primary	Change in Hypoxic Burden (HB) 4%, (scored in reference to AHI 4%), AD109     vs. other 3 study treatments
Secondary	
 
Change in Apnea Hypopnea Index (AHI) 4%
 
Change in Oxygen Desaturation Index (ODI)
 
Total time with SaO2 <90%, PSG nights
 
Proportion of participants with ≥50% reduction, AHI, HB and ODI
 

Exploratory	
 
PSG sleep and arousal parameters
 
PSG respiratory parameters
 

Safety Endpoints	
 
Physical exam, vital signs, clinical laboratory assessment
 
Spontaneous adverse events, including the post-dosing period
 
DSST
 
PSG parameters: heart rate, ECG, EEG, oximetry
 

Abbreviations: AHI = apnea-hypopnea index; DSST = Digit Symbol Substitution Test; ECG = electrocardiogram; EEG = electroencephalogram; HB = Hypoxic Burden; ODI = Oxygen Desaturation Index; OSA = obstructive sleep apnea; PSG = polysomnography; SaO2 = oxygen saturation.

# 4 Study Design

## 4.1 Overall Design

Study APC-003 is a double-blind, placebo-controlled 4-period single dose crossover study designed to demonstrate the individual contribution of atomoxetine and R-oxybutynin to the efficacy of AD109.

Participants will undergo initial pre-screening to determine potential study eligibility. Patients selected for further screening should either have a previous history of OSA of a severity consistent with enrollment criteria or be at high risk (e.g. as assessed by STOP-Bang Questionnaire score). Only patients who meet all non-PSG enrollment criteria at Visit 1 are eligible for a screening PSG. A prior full-night PSG conducted by the study site within 6 months of Visit 1 that meets PSG enrollment criteria can take the place of a screening PSG.

[figure not shown]
Patients who meet all enrollment criteria will be randomized to receive the following experimental treatments, one treatment on each of 4 PSG night:

- Atomoxetine 75 mg + R-oxybutynin 2.5 mg (AD109)
- Atomoxetine 75 mg
- R-oxybutynin 2.5 mg
- Placebo

Dosing of the study treatment will occur immediately prior to lights out. Each morning following PSG exams in the crossover period the DSST will be administered.

Each PSG night is followed by a 1-week washout period. AE/SAE information is recorded at each study visit and by telephone contact with participants during each washout period and at the end of the final washout period. Overall study duration will be up to 14 weeks. A total of 58 participants will be enrolled. Participants who withdraw from the study will not be replaced.

Figure 1: Overview of Study Design

PSG = polysomnography.

## 4.2 Scientific Rationale for Study Design and Dose

Previous Phase 2 studies conducted by Apnimed and academic collaborators support that the combination of atomoxetine and racemic oxybutynin is effective for OSA, and that both drug components are necessary for this efficacy. This factorial study is designed to demonstrate that both atomoxetine and R-oxybutynin contribute to the efficacy of AD109 in OSA. The dose of atomoxetine has been used in previous Phase 2 studies supporting efficacy and safety for OSA in combination with 5 mg racemic oxybutynin. Because the R-enantiomer of oxybutynin confers about 2-fold the anticholinergic activity of the racemate, with such activity thought to be the major contributor to efficacy in OSA, the dose of R-oxybutynin was reduced to 2.5 mg.

A detailed description of the chemistry, pharmacology, efficacy, and safety of AD109 is provided in the Investigator's Brochure.

## 4.3 End of Study Definition

A participant is considered to have completed the study if he/she has completed all phases of the study through the last scheduled procedure shown in the Schedule of Activities (SoA).

The end of the study is defined as the date of the last visit of the last participant in the study or last scheduled procedure shown in the SoA for the last participant in the study globally.

# 5 Study Population

Eligible participants will be recruited both from the existing clinic population at the study sites, including databases of previous subjects who participated in other studies, and through direct advertising to the community.

Participants must be able to provide written consent and meet all the inclusion criteria and none of the exclusion criteria.

#### 5.1 Inclusion Criteria

#### Age and Sex

1. Between 25 to 65 years of age, inclusive, at the Screening Visit.

#### **Objective Disease Measures**

- 2. AHI 10 to <45, or AHI ≥45 if any one of the following criteria are met:
  - a. Fraction of hypopneas (Fhypopnea) is >90% or
  - b. Mean oxygen desaturation of obstructive events is ≤4% or
  - c. Fraction of hypopneas is 50-90% and mean oxygen desaturation is 4-8%

Note: Hypopneas defined by 4% oxygen desaturation

#### Weight

3. BMI between 18.5 and 40.0 kg/m^2, inclusive, at the pre-PSG visit.

#### Male participants:

4. If male and sexually active with female partner(s) of childbearing potential, participant must agree, from Study Day 1 through 1 week after the last dose of study drug, to practice the protocol specified contraception (see Appendix 4: Contraceptive Guidance and Collection of Pregnancy Information).

#### Female participants:

- 5. If a woman of childbearing potential (WOCBP), the participant must agree, from Study Day 1 through 1 week after the last dose of study drug, to practice the protocol specified contraception (See Appendix 4: Contraceptive Guidance and Collection of Pregnancy Information). All WOCBP must have negative result of a serum pregnancy test performed at screening.
- 6. If female and of non-childbearing potential, the participant must be either postmenopausal (defined as age ≥ 55 years with no menses for 12 or more months without an alternative medical cause) or permanently surgically sterile (bilateral oophorectomy, bilateral salpingectomy or hysterectomy).

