#### 5.6 Screen Failures

Screen failures are defined as participants who consent to participate in the clinical study but are not subsequently randomized to study treatment/entered into the study. A minimal set of screen failure information is required to ensure transparent reporting of screen failure participants that meets the Consolidated Standards of Reporting Trials publishing requirements and to respond to

queries from regulatory authorities. Minimal information includes demography, screen failure details, eligibility criteria, and any serious adverse events (SAEs).

Individuals who do not meet the criteria for participation in this study (screen failure) will not be rescreened, except if the opportunity for rescreening has been enabled by protocol amendment.

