# 9.2 Appendix 2: Clinical Laboratory Tests

- The tests detailed in Table 2 will be performed by the central laboratory.
- Laboratory testing is performed non-fasting.
- Additional tests may be performed at any time during the study as determined necessary by the Investigator or required by local regulations.

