# Highly Effective Contraceptive Methods That Are User Dependent

Failure rate of <1% per year when used consistently and correctly.

Combined (estrogen- and progestin-containing) hormonal contraception associated with inhibition of ovulation

- Oral
- Intravaginal
- Transdermal

Progestogen-only hormonal contraception associated with inhibition of ovulation

- Oral
- Injectable

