# Highly Effective Contraceptive Methods That Are User Independent

Implantable progestogen-only hormonal contraception associated with inhibition of ovulation

- IUD
- Intrauterine hormone-releasing system (IUS)
- Bilateral tubal occlusion

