# **Pregnancy Testing**

- WOCBP should only be included after a confirmed menstrual period and a negative highly sensitive serum pregnancy test.
- An additional serum pregnancy testing should be performed at Visit 5 (EOS).

• Pregnancy testing will be performed whenever a menstrual cycle is missed or when pregnancy is otherwise suspected.

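### Required contraception for women of childbearing potential starts only at Study Day 1, and the only scheduled pregnancy test before dosing can be 4 weeks old, so a recent conception could go undetected at the first dose

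*Protocol*

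**What the plan says.** **Contraception.** Inclusion 5 (protocol section 5.1, Female participants) gives the only dated window for WOCBP: "the participant must agree, from Study Day 1 through 1 week after the last dose of study drug, to practice the protocol specified contraception". Section 9.4 (Female Participants) and exclusion 26 require willingness to use contraception but give no start date. The accepted methods fall mainly under two headings in section 9.4, "Highly Effective Contraceptive Methods That Are User Dependent" and "Highly Effective Contraceptive Methods That Are User Independent".

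**Study Day 1.** The protocol does not define it. SAP section 4.6, a data-derivation rule, makes it the randomization date. The Schedule of Activities (protocol section 1.2) marks randomization at V3, and its footnote 5 allows it earlier, once enrollment criteria are met.

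**Pregnancy testing before the first dose.** Inclusion 5 also says: "All WOCBP must have negative result of a serum pregnancy test performed at screening". The Schedule of Activities has one pregnancy-test mark, at V1. Table 2 in section 9.2 likewise places the test at screening and leaves further testing to need. The synopsis gives the length of that period: "Screening, up to 4 weeks".

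**Other safeguards.** Section 9.4 (Pregnancy Testing) asks for a confirmed menstrual period and a negative serum test before inclusion, and for a test when a cycle is missed or pregnancy is suspected. It adds one more serum test at a visit labelled both Visit 5 and EOS. Exclusion 12 bars pregnant women without a date limit. A participant who becomes pregnant is withdrawn.

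**The concern.** Inclusion 5 would be met by a woman who starts a user-dependent method as late as Study Day 1. If she is randomized at V3, no dated requirement covers the time between her V1 test and her first dose, and no further test is scheduled in that time. A conception in that interval could therefore be present, and unknown, when she is dosed. Exclusion 12 would be breached without anyone being aware of it.

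The protocol clearly intends that no pregnant woman be dosed, and section 2.2.3 notes that R-oxybutynin has never been marketed. What is at stake is participant safety. No estimate, test or power figure depends on it.

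**Working it through.** The plan states no figure to reproduce. The check sets the provisions against the time line and adds simple day counts.

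**1. Longest interval from test to dose.** Screening lasts up to 4 weeks: 4 × 7 = 28 days from V1 to V3. If randomization is on the V3 date, inclusion 5 requires contraception on none of the preceding days. If it is earlier under footnote 5, the uncovered period shortens, but the test can still be 28 days old.

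**2. Which safeguards can act before the first dose?**
- *Confirmed menstrual period before inclusion.* Section 5.6 describes screen failures as those "not subsequently randomized to study treatment/entered into the study". If inclusion likewise means randomization, the period precedes randomization. How recent it must be is not stated, and conception can follow it.
- *Missed-cycle or suspicion testing.* This can act between V1 and V3, but only once a cycle is missed and reported.
- *The additional serum test.* V5 in the Schedule of Activities is the third dosing night, and the End of Study Evaluation follows V6. Either way the test comes after the first dose.
- *Exclusions 12 and 26, and the agreement in section 9.4.* None brings a scheduled check at V3.
- *Discretionary tests (section 9.2).* Possible, but not scheduled.

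**3. What missed-cycle testing leaves.** Let menses fall due L days after conception, with L = 14 assumed (range 12 to 16; the documents give no value). A conception d days before V3 shows as a missed cycle before V3 only if d > L. The last L days before V3, 14 (12 to 16), are therefore out of reach. In a 28-day screening the earlier 28 − 14 = 14 days (12 to 16) can be caught, if the missed period is noticed and reported.

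**4. What a V3 test would add.** Assume a test detects from D = 10 days after conception (range 7 to 14, again not in the documents). The V3 test then catches conceptions at least D days old.
- Gain over missed-cycle testing that works as intended: L − D = 14 − 10 = 4 days.
- Smallest: 12 − 14 is negative, so 0. Largest: 16 − 7 = 9.
- If a missed cycle is not noticed or reported, the gain is larger.

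**5. What contraception from V1 would add.** If effective from V1, it prevents conceptions between V1 and V3, including the last D days that a V3 test cannot see. It cannot help with a conception in the D days before V1, too recent for the V1 test: 10 days (7 to 14). A V3 test picks these up if V1 to V3 is at least D days. With both measures nothing is left once the interval is at least 14 days. At a 7-day interval, 10 − 7 = 3 days are left (range 7 − 7 = 0 to 14 − 7 = 7).

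**6. Why the doses before detection cannot be counted.** With minimum 7-day washouts, the earliest dosing days after V3 (day 0) are days 7, 14 and 21. With L = 14 and conception one day before V3, the missed period falls on day 14 − 1 = 13, after two doses. The third dose can follow on day 14. Whether it is given depends on when the missed period is noticed and on how fast the result returns. Serum hCG is a Table 2 test, and section 9.2 says: "The tests detailed in Table 2 will be performed by the central laboratory". The documents give no turnaround time.

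**The case against.** The strongest case against the point is that the protocol already has several layers. Testing on a missed cycle is mandatory. A menstrual period must be confirmed before inclusion. Pregnancy excludes at any time, as does unwillingness to use contraception. Section 9.2 lets the investigator order extra tests at any time. Randomization may precede V3, which brings contraception forward. An earlier start would also bind women who go on to fail screening and never receive drug.

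Much of this stands, and it limits two stronger readings:

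- A reader might infer that any conception during the 28 days would go undetected. The documents do not support that: 28 days is the maximum age of the scheduled test, and missed-cycle testing narrows the unreachable part to roughly the last two weeks.
- A reader might infer that these women are unprotected until Study Day 1. That does not follow either. An implant, an intrauterine device or tubal occlusion would normally already be in place, and the absence of a dated requirement is not the absence of contraception.

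What does not stand is the idea that these layers close the gap. None schedules a check before the first dose, and none can reveal a conception shortly before V3.

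The Visit 5 / EOS label is a separate inconsistency with the Schedule of Activities, which marks no pregnancy test at either point. It does not affect the conclusion here.

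**Conclusion.** The gap is real and narrow. Followed exactly as written, the plan allows a woman who conceives in about the 14 days before V3 (12 to 16) to be dosed while pregnant. This needs a user-dependent method not yet begun, or no method, and it is widest when randomization falls on the V3 date. It also rests on the SAP's reading of Study Day 1, because the protocol gives none.

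The probability cannot be estimated: neither the number of WOCBP nor their contraceptive use is stated. A reader might want an upper limit on doses received before detection, but the documents do not support one, for the reasons in step 6. Missed-cycle testing, the later serum test and withdrawal on pregnancy limit continued dosing without fixing a number.

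The change is worth making because it is cheap and serves what exclusion 12 is there to do. The primary analysis is unaffected.

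**What to change.** **Main change.** In inclusion 5, for WOCBP, replace *from Study Day 1* with *from the screening visit (V1)*, and state the same start in section 9.4 (Female Participants). This also removes the dependence on an undefined day.

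Cost: two wording edits, and up to about 4 more weeks of required contraception, including for some women who later fail screening.

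**Optional addition.** Add a pregnancy test at V3 to the Schedule of Activities, with the result known before dosing. Because Table 2 tests go to the central laboratory, specify one that can be read on site. Cost: one schedule entry and one test per randomized WOCBP. On the assumptions above it adds only about 4 days of coverage (0 to 9) beyond missed-cycle testing that works as intended, and more where a missed cycle is overlooked. It also covers conceptions too recent for the V1 test, which earlier contraception cannot address.
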